Developing Effective Response Inhibition Training for Symptom Relief in OCD and Trichotillomania

NCT02059980

7/1/2018

STUDY PROTOCOL

Effective behavioral and pharmacological treatments exist for obsessive-compulsive disorder (OCD), but a significant portion of patients with OCD refuse to receive, drop out of, or otherwise fail to respond to the currently most efficacious treatments.^{1,2} Suboptimal clinical outcomes and under-utilization of these treatments often result from practical barriers such as adverse effects (e.g., intense distress during the exposure procedure or side effects of medication), high costs, and a lack of trained therapists.³ Despite the demonstrated efficacy of existing treatments, almost half of individuals with OCD continue to suffer from this extremely debilitating condition without adequate treatment. Thus, disseminable and cost-efficient therapeutic approaches with minimal adverse effects are required for OCD. In this regard, a promising therapeutic approach is computerized cognitive retraining which has recently shown success in improving psychiatric conditions by directly modifying biased or deficient cognitive processes that are considered to be central to such conditions.⁴⁻⁶ There is compelling evidence that poor response inhibition (RI) is a core cognitive feature of OCD^{7,8} and is its putative endophenotype.⁹ RI is the basic cognitive ability required to inhibit potent but inappropriate responses,¹⁰ and research indicates that RI can be functionally changed by practice.¹¹ Despite the growing evidence for the significance of poor RI in OCD, it is unknown whether OCD symptoms can be improved using cognitive retraining designed to enhance the individual's RI capabilities. To improve overall treatment response rates in OCD, it is vital to develop an effective intervention with minimal adverse effects that may result in enhanced treatment acceptability, patient retention, and dissemination.

Our long-term goal is to understand how to change anomalous cognitive processes underlying OCD and its related conditions such as trichotillomania (TTM) in order to develop and disseminate effective computer-based cognitive interventions. The objective of the current R21 application is to examine the feasibility of using a computerized RI training (RIT) program to improve OCD-related symptoms. Our central hypothesis is that cognitive training designed to enhance RI will improve this problematic cognitive process in OCD and TTM and produce a significant reduction in OCD/TTM symptoms. This hypothesis is based on (a) existing behavioral, electrophysiological, and neuroimaging data suggesting poor RI as a core feature of OCD and TTM and (b) our preliminary data suggesting that RIT can be a useful therapeutic intervention for OCD and its related conditions characterized by poor RI. The expected results will lay a strong groundwork for future studies at the R01 level aimed at developing, testing and disseminating evidence-based RI-focused cognitive training for OCD that can be used as an adjunctive intervention to enhance existing treatments or as a stand-alone intervention. We propose two specific aims and an exploratory aim for this proposal.

Aim 1. To determine the effectiveness of computerized RIT in enhancing RI among OCD/TTM patients.

We hypothesize that OCD/TTM patients who undergo the 8-session RIT program will show greater RI capabilities, relative to OCD/TTM patients who receive placebo cognitive training.

Aim 2. To determine the utility of computerized RIT in improving OCD/TTM symptoms. We hypothesize that OCD/TTM patients who undergo the 8-session RIT program will show a greater reduction in OCD/TTM symptoms, relative to OCD/TTM patients who receive placebo cognitive training.

Exploratory Aim. To evaluate the subjective treatment experiences and patient retention. To assess the end-user acceptability of the proposed cognitive training program, we will assess treatment acceptability and satisfaction as well as treatment refusal and drop-out rates.

This project is innovative because it uses the approach of a novel cognitive training intervention to directly modify underlying cognitive abilities and improve OCD symptoms. The proposed RIT program has been designed as an engaging and immersive computer game to target a core cognitive deficit of OCD-related conditions, which is also in line with the NIH's growing interest in computer game-based neuropsychiatric intervention. This project is expected to have a positive impact by generating important knowledge that will guide the development of an effective cognitive training program for OCD-related conditions that would potentially result in an effective, cost-efficient, and portable intervention with low adverse effects, or enhance the clinical outcomes of existing treatments as an adjunctive intervention. If successful, this line of translational research is expected to contribute to improving overall treatment response rates among individuals suffering from this debilitating and costly illness, yielding significant public health impact.

APPROACH

Project Overview. Over the course of 2 years, 30 individuals with OCD/TTM will complete either RI Training (RIT; n=15) or Placebo Training (PLT; n=15). At baseline, participants will complete (a) clinician-administered rating and self-report scales for OCD/TTM symptoms, (b) questionnaires for other emotional symptoms, and (c) 3 RI assessment tasks. Participants will then undergo 8-session cognitive training (RIT or PLT) over a 4-week period. Both participants and the independent evaluator (IE) will be blinded to the training condition. Potential adverse events will be assessed weekly during the intervention period by the IE. At post-training, we will re-evaluate participants' symptom severity and RI performance. Treatment acceptability and satisfaction will also be measured at this point. At 1-month follow-up, participants will be assessed again for the severity of OCD/TTM and other emotional symptoms and RI performance (see Figure 1). Regarding the overall timeline of the project, active recruitment will occur in Month 2 through 22 after the initial preparatory work (Month 1). Data analyses and preparation of manuscripts, conference presentations, and a grant application will occur in Month 20 through 24.

[figure not shown]

Figure 1. Overall Study Procedures

RESEARCH DESIGN

Participants. We will recruit 30 individuals who meet the following inclusion criteria: (a) age between 18 and 60, (b) a primary diagnosis of OCD/TTM as determined by the Structured Clinical Interview for DSM-5 (SCID-5), (c) moderate level of OCD or TTM symptoms,⁴⁷ and (d) IQ > 80 (on the Wechsler Abbreviated Scale of Intelligence-II). Exclusion criteria include: (a) current substance abuse/dependence, (b) current or past psychotic disorder, bipolar disorder, or schizophrenia, (c) presence of ADHD, or TS (conditions known for poor RI), (d) severe depressive symptoms (evidence suggests that executive function deficits in OCD are attributable to comorbid depression^{48,49}), (e) current psychotherapy, (f) current psychoactive medications (a variety of pharmacological agents were shown to be implicated in RI, including dopamine, norepinephrine, and serotonin⁵⁰⁻⁵²), and (g) current suicidality.

Cognitive Training Programs. RIT is a 30-level computer game (with a story of defending a village from aliens), designed to offer systematic practice of RI focused primarily on action withholding and cancellation, incorporating parameters of go/no-go and stop-signal tasks. Main task materials are simple geometric figures (e.g, squares, circles). However, RIT is different from a mere repetition of existing go/no-go or stop-signal tasks in several important ways: (a) with ascending levels, RIT becomes more difficult by systematically varying RI

task parameters integrated into each game level (i.e., frequencies of no-go or stop trials, stop-signal latencies, and increased stimulus potency via set switching); (b) RIT guides participants to make individually-tailored progress toward their own levels of challenge (i.e., each level is repeated until high accuracy is reached); (c) RIT contains video-game features to maximize participant's motivation (e.g., engaging story and graphics, and display of record scores); and (d) RIT provides trial-by-trial performance feedback to help participants make conscious efforts to improve their ongoing performance. In each 45-min session, five 7-min game levels are offered with brief inter-level breaks. After completing each level, a result page will summarize the participant's performance. The central training components of RIT are the same as those used in our pilot studies.

Similar to other cognitive retraining paradigms, the RIT is based on the rationale that repeated practice of the core cognitive process central to the condition would result in clinically meaningful improvement. The RIT is expected to allow individuals to practice (a) suppressing pre-potent stimulus-response association, (b) inhibiting potent ongoing response, (c) selectively inhibiting response to inappropriate stimuli, (d) exerting cognitive flexibility to changing targets, and (e) maintaining goal-directed responses in the given context. Based on the evidence suggesting RI as a core feature of OCD and our preliminary data, we predict that RIT will generate meaningful clinical improvement in OCD beyond a simple task practice effect which would improve only RI task performance without affecting OCD symptoms.

Similarly, PLT is a 30-level computer game but presents only go trials, and thus provides no opportunity to practice RI components (i.e., action withholding and cancellation). However, its 30-level structure and task stimuli are identical to those of the RIT program, and they also become increasingly difficult across level (by more abrupt onsets and increasingly shorter duration of the stimuli). We expect PLT to have negligible effects on RI capabilities and OCD symptoms. The RIT/PLT will be administered in a small therapy room at the UWM Psychology Clinic and Anxiety Lab. The participant will complete each training session following the computerized instructions. A trained administrator will be present in all sessions to assist in the event of any technical difficulties.

Primary and Other Outcome Measures

Considering the inclusion of two diagnostic conditions (OCD and TTM), we will obtain clinician-rated symptom ratings for both conditions, using the Yale-Brown Obsessive-Compulsive Scale and the NIMH TTM Symptom Severity Rating Scale. The primary outcome index will be a z-transformed score of the symptom ratings obtained from the two rating scales. We will also use the Clinical Global Impression (CGI) rating scale is a widely used brief assessment tool for evaluating illness severity, global improvement or change, and therapeutic response.

We will also use the stop-signal and go/no-go task, in which participants should promptly indicate the direction (left vs. right) of an arrow on each trial, but inhibit response when an auditory stop signal is presented. Stop Signal Reaction Time (SSRT; time taken to complete the inhibitory process) is estimated using the tracking algorithm, which adjusts the stop signal delay automatically (by 50ms) to maintain the rate of successful inhibition on stop-signal trials at 50%.¹⁰ This particular version has successfully demonstrated the RI deficits in both OCD patients and unaffected first-degree relatives.^{7,43} The SSRT is a behavioral RI outcome measure for this study. The go/no-go task asks participants to quickly press a button for letters (e.g., Q, P, T; go trials) except to the letter X (no-go trial).⁶⁷⁻⁶⁹ Twenty-five percent of the task constitutes no-go trials. The RI index from this task is the number of commission errors. Patients with OCD showed abnormal activity in fronto-striatal circuits while performing this type of go/no-go task.^{35,69}

STATISTICAL ANALYSIS PLAN

Power Analysis. We conducted power analyses using a conventional large effect size ($f = .40$). With $\alpha = .05$, a correlation of .5 among repeated measures, and a nonsphericity correction of .6, the required sample size is 9 per group to achieve the power of .80 in detecting a large group X time interaction effect ($f = .40$). Based on the recommendation from Ukoumunne et al.⁷⁰ that allows standard power analyses to be used for

multilevel models by multiplying the sample size by the design effect, the necessary sample size is 20 after an adjustment by a factor of 1.1, which was derived from an assumed intraclass correlation of .05. Taking into account 25% patient attrition ($n=5$), a total of 25 would offer an adequate sample size to detect a medium to large effect size. Thus, this proposal ($N=30$) is sufficiently powered ($=.90$) to detect a large effect, but is underpowered ($=.50$) to detect a medium effect ($f=.25$).

Specific Aim 1 - To determine the effectiveness of RIT in enhancing RI among OCD/TTM patients. To attain the objective of Aim 1, we will test the working hypothesis that RIT will show greater improvement in RI performance than PLT. Our primary analytic strategy is multilevel modeling, which effectively handles multi-session data with hierarchical structure (i.e., three time points nested in individuals), missing data, and serial correlation. To test the hypothesis, the level-1 intercept will be regressed on training condition to examine group differences, and the slope for time will be regressed on training condition to produce a cross-level interaction to examine the differential rate of change in RI performance between the two groups.

Specific Aim 2 - To determine the utility of the RIT in reducing OCD/TTM symptoms. To attain this objective, we will test the working hypothesis that RIT will show a greater reduction in OCD/TTM symptoms than PLT. Our primary analytic strategy is random effects mixed model analyses, in which the level-1 intercept will be regressed on training condition to examine group differences and the slope for time will be regressed on training condition to produce a cross-level interaction that examines group differences in the rate of change in OCD/TTM symptom z-scores.

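### The readable text schedules adverse-event checks for the 4 training weeks only, about half of the post-baseline period over which efficacy is analysed

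*Combined protocol and SAP*

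**What the plan says.** All the scheduling information is in the Project Overview of the combined protocol and SAP.

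- Treatment period: "Participants will then undergo 8-session cognitive training (RIT or PLT) over a 4-week period".
- Adverse events: "Potential adverse events will be assessed weekly during the intervention period by the IE". The sentence fixes a frequency, an assessor (the blinded independent evaluator) and a window.
- Post-training visit: "At post-training, we will re-evaluate participants' symptom severity and RI performance". Acceptability and satisfaction are added at this visit.
- Follow-up visit: "At 1-month follow-up, participants will be assessed again for the severity of OCD/TTM and other emotional symptoms and RI performance". The sentence then refers to Figure 1.

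In the Statistical Analysis Plan, the Aim 1 model has three time points per person. The Aim 2 model has the same form, with a time slope that may differ by training condition. No section gives an adverse-event analysis, a safety endpoint or a rule for following an event that is still open when training ends. The exploratory aim is limited to the patient's experience and retention: "we will assess treatment acceptability and satisfaction as well as treatment refusal and drop-out rates".

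**The concern.** The adverse-event window is explicit and ends with training. The visits that follow are itemised, and adverse events are on neither list. A site that follows the text would therefore rate symptoms and test response inhibition a month after training without asking whether anything untoward had happened since the last weekly check.

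Two consequences follow. Benefit would be followed for about twice as long as harm, so the trial could report a benefit lasting to 1 month with no matching adverse-event record. An event still open at the last weekly check would also have no planned point at which its outcome is recorded. This matters because the study is meant to lay the groundwork for larger trials, and its adverse-event record is likely to inform them.

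**Working it through.** The documents give no adverse-event rate or safety figure, so there is nothing of the plan's own to reproduce. The check has three parts.

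**1. What each occasion records, from the Project Overview**

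| Occasion | Symptom severity | Response inhibition | Adverse events |
|---|---|---|---|
| Baseline | yes | yes | not listed |
| Weekly, weeks 1 to 4 | not listed | not listed | yes |
| Post-training | yes | yes | not listed |
| 1 month | yes, with other emotional symptoms | yes | not listed |

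**2. Share of post-baseline time covered**

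Inputs: training of 4 weeks = 28 days (stated); follow-up of 1 month (stated, but not defined in days). Assumptions: a month is 28 to 31 days, it runs from the end of training, and the weekly checks account for all 28 training days.

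Coverage = 28 / (28 + follow-up days):

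- 28 days: 28/56 = 50.0%
- 30 days: 28/58 = 48.3%
- 30.44 days: 28/58.44 = 47.9%
- 31 days: 28/59 = 47.5%

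Between 50% and 52.5% of post-baseline time therefore has no scheduled adverse-event question.

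For the planned 30 participants, if all complete, the covered time is 30 × 4 = 120 person-weeks. The total is between 30 × 56/7 = 240 and 30 × 59/7 = 253 person-weeks. Asking at the 1-month visit about the whole interval since the last check would bring coverage per person from 4 weeks to between 56/7 = 8 and 59/7 = 8.4 weeks, which is all of it. Sample size, alpha and power are unaffected.

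**3. From time to events**

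The share of time is not the share of events. If the event rate were constant (an assumption), 50% to 52.5% of post-baseline events would fall after training. If events are confined to the period of exposure, the loss is near zero. If they are delayed, it exceeds half. Nothing in the documents chooses between these cases, so the number of events lost cannot be estimated.

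**The case against.** **Silence is not exclusion.** The Project Overview is a summary paragraph. It does not say that recording stops after training or that a reported event is to be ignored, and Figure 1 might list adverse events at later visits. This stands as a limit on certainty, so the point is confined to the readable text. It does not remove the point: a stated window followed by itemised visits is more specific than general silence, and the text should be clear without the figure.

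**The follow-up month is not blind.** A reader might infer that it goes unobserved. It does not. OCD/TTM severity and other emotional symptoms are measured again at its end, and lasting worsening there is a main plausible harm of a computer game. This objection stands. What remains is structured capture of transient events, events outside those scales, and the outcome of open events.

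**Exposure is fully covered.** Training consists of eight 45-minute sessions with an administrator present, and the weekly checks span all of them. If training-related events occur mostly then, little is lost. This also stands, and is why no event count is claimed.

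**The low-harm wording does not depend on the window.** A reader might infer that a claim of low adverse effects rests on half the observation time. The text says only that the work "would potentially result in an effective, cost-efficient, and portable intervention with low adverse effects". That is a hedged expectation about a future programme, and no adverse-event analysis is planned from which to conclude it. Nor is minimal harm a trial objective: it is motivation in the opening section, while the stated objective is feasibility and the aims concern response inhibition, symptoms, and acceptability and retention.

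**The population should not be made to look more vulnerable than it is.** A reader might take entry to require at least moderate symptoms in patients without other care. The Participants section asks for a moderate level, with no such floor wording. It does exclude current psychotherapy and psychoactive medication, but the same list also excludes severe depressive symptoms, current suicidality, psychotic and bipolar disorder, and substance abuse or dependence.

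**Conclusion.** The point holds in a limited form. On the readable text, structured adverse-event collection covers 47.5% to 50% of the post-baseline period over which efficacy is analysed, and neither of the two later visits is listed as including it. The percentage rests on the stated 4 weeks and an assumed month of 28 to 31 days. The absence at later visits is read from the text alone, without Figure 1.

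The coverage figure describes time. It does not support a statement that half of all events would be missed, since that needs a constant event rate that the documents do not give. The primary outcome, alpha and power are not affected. This is a cheap improvement in harm ascertainment that the sponsor should make, and it does not undermine the efficacy analysis.

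**What to change.** Amend the Project Overview so that the existing weekly adverse-event questions are also asked at post-training and at the 1-month follow-up. Each time they should cover the interval since the last check and the status of any unresolved event. Ask them after that visit's symptom ratings are complete, so that the answers cannot influence the ratings. If Figure 1 already shows this, bring the text into line with it. Add to the Statistical Analysis Plan that participants with at least one event will be reported by arm, from the first session through 1 month.

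The cost is a few minutes at two visits already held, and possibly a slightly higher reported event count.

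Two limits remain. Asking at the visit does not reach someone who misses it, so an event that causes a missed visit would still appear only as missing data. And the arms are small: even with complete collection, no events among 15 trained participants would leave an exact two-sided 95% upper limit of 1 − 0.025^(1/15) = 21.8%. That limit comes from the sample size and not from the collection window, so the by-arm counts should be read as descriptive.

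### Does the primary z-score need a new definition because the plan does not say how the two symptom scales are combined or standardised?

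*Combined protocol and SAP*

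**What the plan says.** Eligibility (Research Design, Participants) asks for "a primary diagnosis of OCD/TTM as determined by the Structured Clinical Interview for DSM-5 (SCID-5") and, as a separate criterion, "c) moderate level of OCD or TTM symptoms". One disorder is therefore enough.

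Primary and Other Outcome Measures opens by giving the presence of two diagnostic groups as its reason for using two instruments. It then says "we will obtain clinician-rated symptom ratings for both conditions", "using the Yale-Brown Obsessive-Compulsive Scale and the NIMH TTM Symptom Severity Rating Scale", and defines the outcome: "The primary outcome index will be a z-transformed score of the symptom ratings obtained from the two rating scales".

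The Statistical Analysis Plan, Specific Aim 2, analyses "group differences in the rate of change in OCD/TTM symptom z-scores" with a random effects model in which the slope on time depends on training condition.

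No section gives a combination rule, a rule for patients with both disorders, or the mean and SD behind the z-score.

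**The concern.** This is the Aim 2 outcome, and two competent analysts could compute it differently. There are three worries.

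- **Dilution.** Read literally, a score from two scales could average in a scale for a disorder the patient does not have. That scale cannot improve much and may only add noise, in a trial of 30 that already puts its power for a medium effect at .50.
- **Lost within-arm change.** If z-scores were formed separately at each visit, the overall mean would be 0 every time. The central hypothesis predicts that training will "produce a significant reduction in OCD/TTM symptoms", and the section on the training programs says "We expect PLT to have negligible effects on RI capabilities and OCD symptoms". Neither statement could be checked on such scores.
- **Choice after the fact.** An open rule lets an analyst try several scorings and keep the most favourable.

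**Working it through.** **1. The plan's own power figures.** Inputs from Power Analysis: f = .40, alpha = .05, correlation .5, nonsphericity .6, two groups; three time points come from Specific Aim 1. For the interaction F test:

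- lambda = f² × N × 3 × .6 / (1 − .5)
- df1 = 2 × .6 = 1.2; df2 = (N − 2) × 2 × .6

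N = 18 gives lambda = 10.37 and power .84; N = 16 gives .79. So 9 per group reproduces. The design effect is 1 + 2 × .05 = 1.1, and 18 × 1.1 = 19.8, so 20 reproduces. For N = 30, the effective size is 30 × .75 / 1.1 = 20.45. Power is then .89 at f = .40 (stated .90) and .51 at f = .25 (stated .50). These figures use a generic f and do not depend on how the z-score is built.

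**2. Own scale against averaged scale.** The documents give no diagnosis mix, scale SDs, comorbidity or off-diagnosis noise, so these are assumptions: half OCD, half TTM; no comorbidity; own-disorder SD 1; off-diagnosis SD k, independent; diagnosis groups 4 SD apart on each scale; arm difference .8 SD at the last visit; 15 per arm; complete data; correlation .5.

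The SD of change on the own scale is sqrt(2 × (1 − .5)) = 1. Adding the off-diagnosis scale makes it sqrt(1 + k²). The standardised effect is d = .8 / sqrt(1 + k²), the noncentrality is d / sqrt(2/15), and the t test has 28 df.

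| Index | d | Noncentrality | Power |
|---|---|---|---|
| Own scale | .80 | 2.19 | .56 |
| Averaged, k = .1 | .80 | 2.18 | .56 |
| Averaged, k = .5 | .72 | 1.96 | .47 |
| Averaged, k = 1 | .57 | 1.55 | .32 |

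Simulation (20,000 trials per cell) agrees: .55, .56, .48 and .32. If off-diagnosis scores sit on a floor, power at k = .5 is .50 to .53, and at k = 1 it is .36 to .44. If both scales respond equally in patients with both disorders, the loss is gone at about 30% comorbid (k = .5) or 50% (k = 1). At 50% comorbid and k = .5 averaging reaches .63, above the own-scale index.

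**3. Why the averaged effect looks so small.** In simulation the z-scale effect falls from −.85 to about −.18. Most of this is a change of units. At k = .5 the pooled SD is sqrt(.5 × (1 + .25) + .25 × 4²) = 2.15, and .8 / 2.15 / 2 = .19. At k = .1 the effect is the same size, .19, yet power is .56, so the shrinkage itself costs no information.

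**4. How the .8 SD compares with the plan's effects.** A difference growing as 0, .4, .8 over three visits leaves interaction deviations of ±.2, 0, ±.2 per arm. Hence f = sqrt((.04 + 0 + .04)/3) = .16, below the plan's .25 and .40. At f = .40 the last-visit difference would be .8 × .40/.163 = 1.96 SD. The same test then gives power of about 1.00 (own scale), 1.00 (k = .5) and .96 (k = 1). With the plan's attrition, design effect and nonsphericity (effective N about 20), f = .40 gives .88. It falls to .80 for f = .40/sqrt(1.25) = .36 and to .60 for f = .40/sqrt(2) = .28.

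**5. Standardising by visit.** If placebo does not change and RIT improves by .8 SD, the visit means become ±.4 / sqrt(1 + .4²) = ±.37. Placebo appears to worsen, which misleads about within-arm change. The arm contrast keeps its sign and type I error; simulated power is .52 against .55.

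**6. Picking a rule afterwards.** Taking the smaller p-value from the own-scale and averaged rules gives a simulated type I error of .06 to .08; over four rules it is .07 to .10.

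**The case for a change.** The strongest case for acting is that the formula for the primary outcome is missing and costs a few sentences to supply. The wording about ratings from two scales can support averaging, and even the own-disorder reading leaves the reference mean and SD open. Blinding is described for participants and the independent evaluator, not for the analyst. In a trial of this size, avoidable noise or a flexible outcome is unwelcome.

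The omission is real, and the selection risk would exist if someone chose the rule after seeing results by arm. It does not follow that the planned analysis is wrong. The outcome section gives the two diagnoses as its reason for using two instruments, which explains a z-score: patients rated on different scales need a common metric. The label OCD/TTM is used throughout for whichever disorder applies. A model for rate of change, with a hypothesis about greater reduction, fits one fixed reference better than a new one at each visit. The raw ratings and the CGI remain available to describe change within each arm.

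Nor is there one clearly better rule to impose. Scoring only the primary-diagnosis scale protects against off-diagnosis noise, but gives up power if many patients have both disorders (.55 against .63 at 50% comorbid and k = .5). Standardising within diagnosis may also rest on a small group: with 5 patients, 95% of sample SDs fall between .35 and 1.67 times the true value.

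**Conclusion.** No change to the plan follows. What is missing is a written scoring definition, which an analyst would sensibly fill with the own-disorder scale and a fixed baseline reference, arms combined. Under that reading the Aim 2 group-by-time test is valid.

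The harm depends on readings the plan does not state. Averaging both scales in single-disorder patients would cost between nothing and a moderate amount of power (.56 down to .32 on the assumed .8 SD difference), and could gain power with enough comorbidity. By-visit scoring would obscure within-arm change without biasing the test between arms. Selecting the better of two rules would raise type I error to .06 to .08, but only if the choice were made on the results.

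Apart from the visit correlation and the group sizes, the inputs to these power figures are assumptions. The conclusion that the gap is modest rests mainly on how the outcome section reads, and less on any one of these figures.

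### Does the Power Analysis overstate what 30 patients can detect by leaving its large and medium effects untranslated and by powering an F test instead of the planned slope test?

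*Combined protocol and SAP*

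**What the plan says.** The Power Analysis section opens with "We conducted power analyses using a conventional large effect size" (f = .40). It assumes alpha = .05, "a correlation of .5 among repeated measures, and a nonsphericity correction of .6", and states that "the required sample size is 9 per group to achieve the power of .80 in detecting a large group X time interaction effect", with f = .40. A design effect of 1.1, from an assumed intraclass correlation of .05, raises the total to 20. An allowance for 25% attrition raises it to 25, and the section comments that "a total of 25 would offer an adequate sample size to detect a medium to large effect size". The next sentence concludes that the planned 30 have power .90 for a large effect, and that this size "is underpowered ($=.50$) to detect a medium effect ($f=.25").

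The analyses are described under Specific Aims 1 and 2. Aim 1 uses a multilevel model, chosen partly because it handles "three time points nested in individuals), missing data, and serial correlation". Aim 2 uses a mixed model in which "the slope for time will be regressed on training condition to produce a cross-level interaction that examines group differences in the rate of change" in symptom z-scores. The Project Overview gives 15 patients per arm, assessed at baseline, post-training and 1-month follow-up.

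**The concern.** Three things look wrong at first.

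1. **Labels.** The words large and medium are attached to f for an interaction with three visits, with no equivalent in SD or scale points. Converted to an arm difference in change, both are bigger than the labels suggest.
2. **Test.** Power is given for a multi-degree-of-freedom group by time F test with a nonsphericity correction. The planned test is a single contrast, the effect of condition on the slope.
3. **The figure of 25.** It was derived from f = .40 alone, yet it is called adequate for effects down to medium. The next sentence says that even 30 is not enough for a medium effect.

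What would be at stake is interpretation. The study is meant to prepare the ground for larger trials. A null result from a trial described as sufficiently powered could be taken as evidence against differences of about 1 SD, which it could easily miss.

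**Working it through.** **Inputs.** From the Power Analysis section: f = .40 and .25, alpha = .05, correlation ρ = .5, nonsphericity ε = .6, design effect 1.1, attrition 25%. From Specific Aim 1: m = 3 visits. From the Project Overview: two arms of 15.

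**Step 1: reproduce the plan's figures.** For the group by time F test, λ = f²·N·m·ε/(1 − ρ), df1 = (m − 1)ε = 1.2 and df2 = (N − 2)(m − 1)ε.

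- N = 16, f = .40: λ = .16 × 16 × 3 × .6/.5 = 9.22, power .789.
- N = 18, f = .40: λ = 10.37, power .841. So 9 per group is confirmed.
- Design effect: 1 + 2 × .05 = 1.1, and 18 × 1.1 = 19.8, rounded to 20.
- Attrition: 20 × 1.25 = 25. Dividing instead gives 20/.75 = 26.7, or 27, which is still below 30.
- N = 30 as planned: 30 × .75/1.1 = 20.45 effective. Power is .889 for f = .40 (stated .90) and .506 for f = .25 (stated .50).

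Other scalings of f do not fit. Partial-eta-squared and Cohen-type scalings need 46 to 48 patients in total. Assuming sphericity, or leaving ε out of λ, needs only 12.

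**Step 2: translate f.** Let D be the arm difference in change, in units of the outcome SD at one visit. The interaction residuals are ±D/2 times the centred time pattern.

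- Reached at post-training and kept (0, 1, 1): the centred squares average 2/9, so f² = D²/18 and D = f√18.
- Linear to follow-up (0, .5, 1): the centred squares average 1/6, so f² = D²/24 and D = f√24.

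| f | kept from post-training | linear, at follow-up |
|---|---|---|
| .40 | 1.70 SD | 1.96 SD (0.98 at post-training) |
| .25 | 1.06 SD | 1.22 SD |

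**Step 3: power of the slope test.** With about equally spaced visits, the slope contrast is follow-up minus baseline. Its variance is 2(1 − r) SD² per patient, where r is the baseline to follow-up correlation. The standard error of the arm difference is √(4 × 2(1 − r)/N), and power comes from the noncentral t with N − 2 df at N = 20.45.

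- *Equal correlations of .5:* SE = √(4/20.45) = 0.442 SD.
- *Falling correlation (adjacent .705, baseline to follow-up .09):* SE = √(4 × 1.82/20.45) = 0.597 SD. The mean correlation is .5 and ε = .598, so this pattern matches the plan's two summary figures.

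| | plan's F test | slope, equal correlations | slope, falling correlation |
|---|---|---|---|
| f = .40 | .89 | .95 to .99 | .77 to .88 |
| f = .25 | .51 | .62 to .75 | .39 to .49 |

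Both correlation patterns are assumptions. Equal correlations imply ε = 1, not .6. The falling pattern puts .91 of the within-patient contrast variance on the linear contrast, close to the worst case for ε = .6.

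**Step 4: the 25-patient phrase.** After 25% attrition, 25 enrolled leave 18.75, or 17.05 after dividing by 1.1. The plan's F test then has power .82 to .86 for f = .40 and .43 to .47 for f = .25. At 17.05, power .80 is reached at f = .39. So 25 is adequate for a large effect and not for a medium one.

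**The case for a change.** The best case for a change is that a one-paragraph rewording costs nothing and removes a plain inconsistency. Adjacent sentences call 25 adequate for a medium to large effect and 30 underpowered for a medium one. A reader also cannot see from the text that .90 power refers to a difference of 1.7 SD or more, or what power the slope test has. The plan mentions serial correlation, so the less favourable pattern is not far-fetched.

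Some of this stands. The phrase about 25 is wrong, and SD equivalents would help a reader. The rest does not lead to a change:

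- The plan claims a convention for f = .40, not a clinical magnitude, and it gives every input needed for the conversion.
- The feared misreading concerns differences of about 1 SD. On the same conversion, that is f = .25 or slightly less, and the plan already reports power of .50 for f = .25.
- Slope-test power cannot be pinned down from an average correlation and ε. Text assuming equal correlations of .5 would sit beside a nonsphericity of .6 that contradicts it.
- A promised confidence-interval half-width has the same difficulty. For completers it is 0.88 to 0.93 SD with equal correlations and 1.18 to 1.25 SD with falling correlation. Nothing in the plan prevents the interval from being reported.

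**Conclusion.** No change follows. The sample size arithmetic is sound: on the plan's own assumptions, 30 patients give the stated .90 and .50 to within about one point. The mismatch between the powered test and the planned one has no settled direction: at f = .40, slope power runs from .77 to .99 against .89, depending on a correlation pattern that the documents do not give. These slope figures assume an effect that is kept or grows to follow-up. An effect that faded after training would be picked up less well by a slope.

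The remark about 25 patients is a slip of wording: .43 to .47 power at f = .25 is not adequate. But 25 is an intermediate figure, the trial enrols 30, and the following sentence states the position for 30 correctly. Rewording it would alter neither the enrolment, the analysis, nor what the trial can conclude. Anyone reading a null result should bear in mind that medium here means a difference of about 1.1 to 1.2 SD, for which the plan itself reports even odds of detection.
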